3.3 Objectives

Feasibility objectives

An internal pilot study to determine the feasibility of a full-scale trial, in terms of:

- Site set up
- Participant recruitment
- Retention and Cobb angle collection (primary outcome)
- Intervention delivery
- Minimum wear time in NTB arm
- Minimum wear time in FTB arm
- Compliance data

Study Objectives

- To determine if NTB is not inferior to FTB in reducing the risk of curve progression to 50 degrees before skeletal maturity;
- To determine if there is a difference in anxiety, depression and quality of life between NTB and FTB;
- To determine the patient's and parents' experience and satisfaction of the braces;
- To determine the longer-term effects of bracing on quality of life and curve progression up to two years after skeletal maturity.
- To evaluate the relative cost-effectiveness of NTB compared to FTB.

4. Trial Design

A multicentre, prospective, parallel group, pragmatic, non-blinded, randomised controlled non-inferiority trial. The trial will be conducted in a minimum of 19 hospitals. Patients with AIS will be identified within the clinic setting - these will either be new patients or those already seeking treatment for AIS, but haven't yet met the threshold for bracing. Eligibility will be confirmed by the site researcher and information given. Participants will be given time to consider the interventions following receipt of information on both the FTB and NTB. Written consent will be taken online via a remote pathway, after all questions have been addressed. Randomisation will then ensue. Consenting participants will be randomised to receive either FTB or NTB. Follow up will be undertaken in three phases phase 1 (pre-skeletal maturity), phase 2 (post skeletal maturity) and phase 3 (10 year long-term follow-up, to be covered under different project approvals).

An 18-month internal pilot, with clear progression criteria, will follow the recommendations of Avery et al (36) and assess feasibility of the RCT.

[figure not shown]

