5.1 Inclusion criteria

In order to be eligible for the study, all the following criteria must be met at the point of randomisation:

- 1. Participants aged 10-15 years inclusive;
- 2. Diagnosis of adolescent idiopathic scoliosis (AIS) based on:
 - a. No other cause of scoliosis from the patient history; and
 - A normal neurological examination (no MRI scan required) or normal MRI scan (dilated central canal not considered to be a syringomyelia is acceptable);
- 3. Risser stage 0, 1 or 2;
- 4. Curve size (Cobb angle) between 20 and 40 degrees at baseline;
- 5. Curve apex at or below T7;
- 6. Have a good level of understanding of the English language, as trial materials are only provided in English.

Where radiological criteria are close to eligibility limits, confirmation from another consultant is advised.

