6.5 Other Treatments

Patients will we allowed to have other care such as physiotherapy but this will be recorded. Surgical treatment will not be offered unless the curve gets to 50 degrees as determined by the Radiographic Adjudication Committee (RAC).

7. Randomisation and enrolment

Once eligibility has been confirmed, consent acquired and baseline data taken the participant will be randomly allocated to either the treatment arm (NTB) or the control arm (FTB) on a 1:1 basis, using a web-based system provided by the Sheffield Clinical

Trials Research Unit (CTRU). Patient details (ID, date of birth and stratification information) will be entered into the randomisation system and the treatment allocation will be returned. Randomisation will be completed using minimisation based on site, skeletal maturity (Risser score 0, 1 or 2, and curve size (20-30, 31-40 degrees). Randomisation will be done by site staff. Patients and their parents will be informed of their trial allocation, confirmed by SMS or email, followed by a letter. Their GP will also be informed of their participation in the trial, and their treatment allocation.

8. Outcomes

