11.1 Sample size

In the BrAIST trial 28% of braced patients progressed to 50 degrees or more before skeletal maturity, which was the primary endpoint (5), so assuming this for the FTB group, with a non-inferiority margin of 11%, 90% power, 2.5% one-sided significance level and 10% attrition, the study will require 780 participants (390 per group).

This margin was chosen based on participants and parents. They have stated there is considerable functional and psychological benefit from not wearing braces during the daytime. During both PPI focus groups patients have expressed mixed views about FTB, which some were being treated with, and the concept of NTB. Approximately 50% of the group expressed a preference for a NTB. In our SAUK survey, 60% said

they would prefer a NTB compared to 27% for a FTB (and 7% no brace, 6% no answer).

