11.2 Statistical Analysis

The trial will be analysed and reported according to CONSORT guidelines for noninferiority designs (54).

The ITT population (and safety) populations will consist of all participants who consent and are randomised to receive FTB or NTB.

The per protocol (PP) will be defined for participants in the FTB group, as

receiving the FTB treatment as documented in the study protocol (see Section 6)
 Complying and adhering to the treatment they were assigned to. Compliance with FTB would mean wearing the brace for average of >12.9hrs/day (= >65% of the minimum prescribed time) over the post-randomisation follow-up period.

For the NTB group, the PP population will be defined as

1) receiving the NTB treatment as documented in the study protocol

2) Complying and adhering to the treatment they were assigned to. Compliance with NTB would mean wearing the brace for average of >5.2hrs/day (= >65% of the minimum prescribed time) over the post-randomisation follow-up period.

Patients who cross-over from NTB to FTB will be removed from the PP population for the analysis of the primary outcome.

The binary primary outcome is curve progression to 50 degrees or more (treatment failure) before skeletal maturity and skeletal maturity without this degree of curve progression (treatment success). Non-inferiority for the primary outcome will be declared if the two-sided 95% confidence interval (equivalent to a one-sided 97.5%) for the risk difference in the event rate of progression to 50 degrees between the NTB group and the FTB group does not exceed 11%. The analysis will be completed using a Generalized Linear Model (GLM) with binomially distributed response and identity link (55) adjusted for baseline covariates (site, skeletal maturity Risser score 0, 1 or 2, and Cobb angle). This will be conducted on both an intention-to-treat (ITT) population and per protocol (PP) basis. The adjusted differences in failure rates, along with 95% con-fidence intervals will be calculated and presented.

Missing data

For the primary outcome, curve progression to 50 degrees or more (treatment failure) and skeletal maturity without this degree of curve progression (treatment success) any missing outcome data will be imputed through a default "worst" case scenario (i.e. assume treatment failure) and "best" case scenario (i.e. assume treatment success) and the results compared with the available data analysis.

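### The primary identity-link binomial model, with fixed terms for at least 19 sites and an unbanded Cobb angle, will often have no valid maximum-likelihood fit if baseline Cobb is prognostic

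*Protocol*

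**What the plan says.** Section 11.2 makes the primary analysis a "Generalized Linear Model (GLM) with binomially distributed response and identity link (55) adjusted for baseline covariates". The covariates are "site, skeletal maturity Risser score 0, 1 or 2, and Cobb angle". Non-inferiority is declared if the two-sided 95% interval for the risk difference in failure, NTB against FTB, does not exceed 11%. The same model is used for the ITT and per-protocol populations.

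Section 4 sets the number of sites: "The trial will be conducted in a minimum of 19 hospitals". Entry requires "Curve size (Cobb angle) between 20 and 40 degrees at baseline" (section 5.1), and failure is a curve of 50 degrees or more before skeletal maturity (section 8.1). Minimisation in section 7 uses two Cobb bands, but section 11.2 gives no bands for the primary model. A random site effect is stated only for the secondary longitudinal Cobb analysis.

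For planning, section 11.1 states: "In the BrAIST trial 28% of braced patients progressed to 50 degrees or more before skeletal maturity". It continues "with a non-inferiority margin of 11%, 90% power, 2.5% one-sided significance level and 10% attrition", and concludes that "the study will require 780 participants (390 per group").

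Section 11.2 leaves detailed methods to a SAP to be written before the data are analysed. That SAP is not available here.

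**The concern.** Under an identity link each covariate adds or subtracts percentage points of risk, and nothing keeps the sum above zero. Starting from about 28%, a small curve, Risser 2 and a low-risk site can together take the fitted risk to zero or below. The likelihood then has no maximum at which all fitted risks are valid. Software fails to converge, stops on the boundary, or returns risks outside 0–1. The usual Wald interval rests on an interior maximum, so it is not justified in those cases, yet it is the interval compared with 11%.

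The protocol's own design suggests that Cobb matters. A child entering at 40 degrees needs 10 degrees of progression to fail; one entering at 20 needs 30. Cobb and Risser are both minimisation factors. At stake is whether the analysis that decides the trial can be carried out as written and whether its error rate is the stated one.

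**Working it through.** **1. The plan's own figure.** Inputs from section 11.1: 28% in both arms, margin 0.11, one-sided 2.5%, power 90%, attrition 10%.

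n per arm = (1.960 + 1.282)² × 2 × 0.28 × 0.72 / 0.11² = 10.507 × 0.4032 / 0.0121 = 350.1, so 351. Then 351 / 0.9 = 390 per arm, 780 in total, which matches. Analysed: 2 × 351 = 702. Planning SE = √(0.4032 / 351) = 0.034.

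**2. Size of the model.** 19 sites give 18 site contrasts, plus two Risser terms, one Cobb slope and treatment. Equal sites would hold 702 / 19 ≈ 37 patients each.

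**3. Why fitted risks reach zero: a rough hand calculation.** Assume a mild gradient: 21% risk below 25 degrees against 36% above 35, and 32% against 22% across Risser stages.
- Band midpoints 22.5 and 37.5 give 15 points over 15 degrees, so 1 point per degree. A 20-degree curve is 10 points below a 30-degree one.
- Risser 2 is 28 − 22 = 6 points below average.
- The low-risk corner is 28 − 10 − 6 = 12%.
- A site of 37 has an SE of √(0.28 × 0.72 / 37) = 7.4 points, so a site estimated 12 / 7.4 = 1.6 SE low puts that corner at zero.
- The chance per site is about 5.2%. Over 19 sites it is 1 − 0.948¹⁹ ≈ 64%.

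This ignores error in the slopes and assumes that each site has a patient near the corner. It shows the mechanism and the order of magnitude.

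Sites with no failures matter only if some sites are small: 0.72³⁷ is about 0.000005, 0.72¹² about 2%, and 0.72⁵ about 19%.

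**4. Simulation.** 702 analysed, 19 fixed site terms, overall risk 28%, 100–200 runs per setting. Assumed, because the protocol does not give them: Risser split 50/25/25, Cobb uniform on 20–40, the gradients, site sizes and site variation. Failure means no interior maximum with all fitted risks in (0,1). Odds ratios (OR) are per 10 degrees of Cobb.

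| Assumed truth | No valid interior fit |
|---|---|
| No Cobb or Risser effect | 4–45%, depending on site sizes and site variation |
| OR 1.5 (20% at 20 degrees, 37% at 40), without to with OR 1.5 per Risser stage | 25–73% equal sites; 57–82% unequal |
| 21% v 36% by Cobb, 32% v 22% by Risser, unequal sites | 75–84% |
| OR 2 (16% to 43%), without to with Risser | 58–94% equal; 85–95% unequal |
| 17% v 40% by Cobb, unequal sites | 97–99% |
| OR 3 (11% to 52%) | 97–100% |
| Final Cobb = baseline + normal progression, no site or Risser effect | 100% at progression SD 8–12 degrees; 93% at 15; 80% at 20; 50% at 30 |

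With 25 sites, OR 2 and a Risser effect, the rate is 98–99%. Without site terms it is 0–8% up to OR 2, so the site terms are the main driver. In the progression model, an assumed per-protocol set of 400 gives 83–100%, against 50–100% at 702.

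**5. What software returns.** At OR 2 with OR 1.5 per Risser stage and site SD 0.2 on the logit scale, a standard GLM routine failed or did not converge in 30% of runs, and 95% gave fitted risks outside 0–1. In runs with a true difference of 11%, convergence fell from 86% to 49% as gradients and site imbalance rose.

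**6. Error rate.** True difference 11%, uneven sites, 200 runs per setting, standard routine. False non-inferiority was about 2.5% at OR 1–1.5 (91–99% converged), about 6% at OR 2 (76–83%) and about 13% at OR 3 (67–76%). Monte Carlo SE, √(p(1 − p)/200), is about 1.1, 1.7 and 2.4 points.

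**7. The alternative.** Logistic regression with the same covariates, standardised to a risk difference, with OR 2, OR 1.5 per Risser stage and site SD 0.2: 0 of 150 fits failed. Mean SE was 0.033 (empirical SD 0.035), coverage 95% and power 88%, against 89% unadjusted (Monte Carlo SE about 2.6 points).

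**The case against.** Four objections carry weight.

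- **Fixed site terms are inferred.** Section 11.2 says only that the model adjusts for site. A plain GLM has no random effects, so fixed terms are the natural reading, but they are not stated, and they drive most of the result.
- **The gradients are assumed.** The protocol gives no Cobb or Risser effect and no site sizes. With no such effects and equal sites, failure is only about 4–10%. A reader might infer that the model cannot be fitted at all; the protocol does not support that. Direction and plausibility come from the 50-degree threshold, but the size of the effect is unknown.
- **No interior fit does not mean no output.** Software often returns an estimate, and under mild gradients its false non-inferiority rate was near nominal. The inflation was seen only under steeper gradients, in few runs, and those runs do not separate boundary trouble from a non-additive treatment effect.
- **The SAP may already handle this.** A reader might infer that the estimator would be chosen after unblinding. That is unsupported: section 11.2 promises a SAP written before analysis and approved by the TSC and DMEC, and section 4.1 keeps the statisticians blinded until database freeze. The absence of a fallback from the protocol is not a fault.

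It is also not true that any repair would abandon the minimisation factors. Banding Cobb as in section 7, pooling small sites or using random site effects would keep them represented. What stands is that the protocol names a specific primary model that would probably misbehave if followed.

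**Conclusion.** The point holds in conditional form. If site enters as fixed terms and baseline Cobb is prognostic, the named model will often lack an interior maximum-likelihood fit at about 702 analysed: roughly 65–85% of trials under mild Cobb and Risser gradients and over 90% under steeper ones, against 4–45% with neither effect. The practical consequences are non-convergence in a material share of trials, fitted risks outside 0–1, and an interval of doubtful validity against the 11% margin. The evidence on error rates is thin: near nominal under mild gradients, about 6% at OR 2, and around 10–13% under the steepest. A smaller per-protocol set makes matters worse.

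The margin, the risk-difference scale and the sample size of 780 are sound. This should be fixed, with moderate confidence; it does not show that the trial's conclusion would be wrong.

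**What to change.** In section 11.2, name as primary a logistic regression on treatment, site, Risser score and continuous Cobb angle. Standardise it to the marginal risk difference (mean predicted risk under NTB minus mean predicted risk under FTB, over all analysed participants), with a delta-method or bootstrap 95% interval compared with 11%. State a rule, fixed in advance, for pooling very small sites. Keep the unadjusted risk difference as a sensitivity analysis. Apply the same model to ITT and per-protocol, and align the SAP.

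The cost is a short amendment and slightly more analysis work in standard software. The target must be stated as the marginal risk difference, which equals the identity-link coefficient only if the treatment effect is additive across covariates. Covariates, margin and sample size stay as they are.

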8.1 Primary outcome/endpoint

The binary primary outcome is curve progression to 50 degrees or more (treatment failure) before skeletal maturity (Risser stage 4 in girls and Risser stage 5 in boys and skeletal maturity without this degree of curve progression (treatment success).

A Radiographic Adjudication Committee (RAC) will review patients considered to have reached or come close to reaching the primary outcome:

- 1. If the Spinal Team measures the Cobb angle over 45 degrees:
 - a. The patient is informed that the curve has reached a point where RAC assessment is needed. The patient is advised to continue wearing the brace and a provisional plan is made if the RAC reports an angle of 50 degrees or more.
 - b. The image is sent by Image Exchange Portal (IEP) and measured by the RAC and the angle is reported back to the clinical team who will inform the patient. The RAC will be blinded to treatment allocation
- 2. If the Spinal Team suspects the patient may have reached Risser stage 4 in girls and Risser stage 5 in boys:
 - a. The patient is informed that they may have reached skeletal maturity and RAC assessment is needed. The patient is advised to continue wearing the brace and a provisional plan is made if the RAC reports skeletal maturity.
 - b. The image is sent by IEP and assessed by the RAC and the Risser stage is reported back to the clinical team who will inform the patient. If in doubt, it will be concluded that the primary outcome has not been reached and the patient remains in brace for a further 6 months. The RAC will be blinded to treatment allocation.

If a curve measures 50 degrees or more at the same visit that skeletal maturity is reached, the patient will be recorded as having progressed to 50 degrees or more before skeletal maturity.

In order to coordinate RAC review and centralized measurement of spinal x-rays, images will be transferred from each site to the lead site (Sheffield Children's Hospital) via IEP transfer. Trial participants will be added to the Sheffield Children's Hospital patient records system, with the minimum information required (name, NHS number and date of birth), so that once the images arrive, they can be assigned to the patient's record. No other medical information will be added to their patient record. A member of the research team at Sheffield Children's Hospital will then download images for RAC review, and anonymise these, so that they are only identifiable by the study ID number.

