9.1 Study assessments schedule

Data collection will follow the following schedule to the point of surgery (for those patients who have surgery):

	Phase 1 (pre-skeletal maturity)		Phase 2 (2 years post skel- etal maturity)		Phase 3 (long term)	
	Screening	Baseline/ randomisation	Every 6 months, until skeletal ma- turity	12 months post skele- tal maturity	24 monthly post skele- tal maturity	10 years post skele- tal maturity
	CI	inical		-		
Screening form/log (baseline visit)	MN/IP	-	-	-	-	-
Eligibility form	MN	-	-	-	-	-
Informed consent form	E	-	-	-	-	-
Demographics (age, sex, diagnosis, medical history, medication)	MN	-	-	-	-	-
Height, weight	IP	-	IP	IP	IP	-
Cobb angle, Risser stage	MN (pre ra	andomisation)	CT/RAC	CT/RAC	CT/RAC	-
Additional radiological measures (curve type, curve apex etc)	СТ	-	СТ	СТ	СТ	-
Need for surgery	-	-	MN	MN	MN	E
In-brace correction	-	CT (0-6 weeks aft ting		-	-	-
Compliance	-	-	SEN	-	-	-
Treatment switching	-	-	MN	-	-	-
	Patient repo	orted measures				
SRS-22, CHU9D, RCADS 25, PROMIS sleep x2	-	IP/E	IP/E	IP/E	IP/E	E
BSSQ, OPUS CSD (whilst in brace only)	-	IP/E	IP/E	-	-	-
Educational information (summer of year 11)	-	-	E~	E~	E~	E~
Other treatments prescribed to treat scoliosis	-	IP/E	IP/E	IP/E	IP/E	-
	Parent qu	lestionnaires				
Ethnicity	-	E	-	-	-	-
Resource Use Questionnaire	-	E	E	E	E	E#
Patient Cost Questionnaire	-	E	-	-	-	-

School attendance	-	E	E	-	-	-
Harms						
Complications and SAEs	-	-	IP/E	E	E	E

MN = medical notes or BSR form, IP = in-person, RAC = radiographic adjudication committee, E = Electronic, online via an email link sent to the patient (may be chased by mail or telephone), CT = central team, SEN = sensor, implanted into brace. ~ collected summer of year 11, age 16, independent of where the patient is in the study # completed by the patient at 10 years

NB. The screening log will capture the details of any patient who has had the trial discussed with them. This allows capture of information relating to reasons for non-participation, and also dates of contact for reporting in line with CONSORT.

X-rays are intended to be in line with the frequency in standard care, however, it may be that at some centres, a maximum of 4 additional x-rays are undertaken in some patients if their usual care differs.

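### Sex decides at which Risser stage the primary outcome window closes, but the fixed covariate list of the primary model leaves it out: a small loss of precision in ITT and a possible source of bias in PP

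*Protocol*

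**What the plan says.** Section 8.1 defines failure as progression to 50 degrees or more "before skeletal maturity (Risser stage 4 in girls and Risser stage 5 in boys"; reaching that stage below 50 degrees is success. Section 6.3 (Both braces) continues bracing to the same sex-specific stages.

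Section 11.2 analyses this outcome with a "Generalized Linear Model (GLM) with binomially distributed response and identity link", "adjusted for baseline covariates (site, skeletal maturity Risser score 0, 1 or 2, and Cobb angle"), in both the ITT and the PP population. The list is closed. By contrast, the list for the Cobb angle mixed model in the same section is given by way of example.

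Section 7 (Randomisation and enrolment) says: "Randomisation will be completed using minimisation based on site, skeletal maturity (Risser score 0, 1 or 2, and curve size (20-30, 31-40 degrees"). Sex is therefore neither a balancing factor nor a covariate. The schedule in Section 9.1 does collect it at screening: "Demographics (age, sex, diagnosis, medical history, medication").

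**The concern.** Take a boy and a girl with the same baseline Cobb angle and Risser stage. If each curve reaches 50 degrees between Risser 4 and Risser 5, the boy is a failure, while the girl has already been counted a success. Section 9 (Phase 2) itself notes that some curves keep progressing after maturity as the protocol defines it. Baseline Risser stage and Cobb angle cannot carry this difference, because the two children share those values and still have different closing stages.

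A baseline variable that is built into the outcome definition and already collected is a natural covariate. Leaving it out has two consequences:

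- **ITT:** some explainable variance stays in the error term, and any chance difference between arms in the share of boys stays in the estimate.
- **PP:** the population is formed after randomisation, so a difference between arms in the share of boys need not be chance.

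**Working it through.** **Inputs from the protocol (Section 11.1).** "In the BrAIST trial 28% of braced patients progressed to 50 degrees or more before skeletal maturity", taken as the full-time brace rate; design "with a non-inferiority margin of 11%, 90% power", "2.5% one-sided significance level and 10% attrition"; 780 participants, 390 per group.

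**Inputs that the protocol does not give.** The share of boys, *s*, and the boy-girl difference in failure risk, *d*. I assume *s* = 10-30% and *d* = 5-20 points.

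**1. The plan's own figure.** Outcome variance = 0.28 × 0.72 = 0.2016.

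n per arm = 2 × 0.2016 × (1.960 + 1.282)² / 0.11², rounded up, = 351. Then 351 / 0.9 = 390 per arm, 780 in total. The stated size reproduces exactly.

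Standard error of the risk difference = √(2 × 0.2016 / 351) = 0.0339, or 3.4 points. Power = Φ(0.11 / 0.0339 − 1.96) = 90.1%.

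**2. Effect of adjusting for sex in ITT.** Residual variance = 0.2016 − s(1 − s)d². Chance imbalance in the share of boys has SD √(2s(1 − s) / 351), and it moves the unadjusted risk difference by that SD × d.

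Worked case, s = 15%, d = 15 points:

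- variance removed = 0.1275 × 0.0225 = 0.00287, which is 1.4% of 0.2016;
- standard error = √(2 × 0.19873 / 351) = 0.03365, so power is 90.5%;
- SD of imbalance = √(2 × 0.1275 / 351) = 2.7 points, so SD of the shift = 2.7 × 0.15 = 0.40 points.

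| s | d (points) | Variance removed | Power at 351 per arm | Total N for 90% power | SD of shift (points) |
|---|---|---|---|---|---|
| 10% | 5 | 0.1% | 90.1% | 778 | 0.11 |
| 10% | 20 | 1.8% | 90.6% | 766 | 0.45 |
| 15% | 15 | 1.4% | 90.5% | 770 | 0.40 |
| 20% | 20 | 3.2% | 91.0% | 756 | 0.60 |
| 30% | 5 | 0.3% | 90.1% | 778 | 0.17 |
| 30% | 20 | 4.2% | 91.2% | 748 | 0.69 |

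Even at an extreme gap of 30 points, power is 91.2% to 92.6%. These gains ignore variance already explained by Risser stage, Cobb angle and site, so they are approximate.

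**3. Check by simulation.** 20,000 trials per setting, 351 per arm, linear probability model with robust standard errors. The mean estimate was on target with and without sex.

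| s, d | Type I error at the margin, without / with sex | Power, without / with sex |
|---|---|---|
| 15%, 15 points | 2.6% / 2.7% | 90.0% / 90.4% |
| 20%, 20 points | 2.6% / 2.6% | 90.3% / 91.1% |
| 20%, 30 points | 2.4% / 2.4% | 90.0% / 92.1% |

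**4. PP.** Section 11.2 selects on average wear above 12.9 hours a day in one arm and above 5.2 in the other, and removes participants who cross from night-time to full-time bracing. If this leaves a difference in the share of boys, the bias from sex is that difference × d. As an assumed illustration only, 10 points × 0.15 = 1.5 points, and 1.5 / 11 = 14% of the margin. The inverse probability weighting in Section 11.2 is described for the time-to-event and cross-over analyses, not for this binomial model.

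**The case against.** The covariates are the minimisation factors, which is a coherent pre-specified rule, and one more prognostic covariate can look like a matter of taste. The protocol gives no share of boys, no failure rate by sex and no time to maturity by sex; its only duration is a pooled 28 ± 9 months. A risk gap near zero is compatible with the documents, and adjustment would then gain almost nothing. All of this stands, and it limits the size of the point.

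Three stronger readings are tempting and are not supported:

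- **That the ITT result is biased or its error rate inflated.** Randomisation leaves sex to chance, and the confidence interval already covers that chance. The simulation shows no bias and a type I error of 2.4-2.7% either way.
- **That boys are known to be at higher risk.** A longer window is an inference from the definition, and a higher failure rate is a further step that the protocol does not document.
- **That the Cobb angle mixed model and the time-to-event analysis are also deficient.** The first has an open covariate list. The protocol fixes no covariates for the second and leaves detailed methods to the SAP.

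It is also fair that the change is not entirely free. An identity-link binomial model adjusted for site across at least 19 hospitals may already fail to converge or give fitted risks outside 0-1, and each further term adds to that. The site terms are the main strain, however; one binary covariate adds little.

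**Conclusion.** The point holds as a minor one. The outcome window closes at a sex-specific stage by definition, sex is collected at baseline, and the closed list for the primary model omits it.

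In ITT the cost is precision only: 0.1-4.2% of outcome variance and up to about 1 point of power, for an assumed 10-30% boys and a gap of 5-20 points. The unadjusted chance shift has an SD of 0.1-0.7 points, against a standard error of 3.4 and a margin of 11. The sample size of 780 is not called into question.

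In PP, selection after randomisation means that an imbalance in sex could bias the estimate. The documents give no adherence by sex, so whether and how far this happens is unknown.

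**What to change.** Before the statisticians are unblinded at database freeze (Section 4.1), add sex to the pre-specified covariates of the primary ITT and PP binomial models. Adding it after an imbalance had been seen would be open to challenge.

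At the same time, name a fallback in case the identity-link model does not converge. It should still estimate the risk difference, so that the 11-point margin keeps its meaning; standardisation from a logistic model is one example.

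Minimisation, data collection and sample size stay as they are. The cost is one more term in a model that already carries at least 19 sites. In PP, adjustment removes only the imbalance due to sex; other selection by adherence remains.
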